8.4 Demographic and Other Baseline Characteristics

All demographic and baseline summaries will be displayed for the ITT and RCC populations.

Gender, race, ethnicity, will be summarized using counts and percentages. Age (at date of cryoprocedure, computed using the date of birth), height, weight and BMI will be summarized with descriptive statistics (number of patients [n], mean, standard deviation (SD), median, 25th percentile (p25), 75th percentile (p75) minimum (min), and maximum (max)). Age group (≥ 18 to < 65 years, ≥ 65 to < 75 years, and ≥ 75 years) will be summarized using counts and percentages.

The ASA physical status classification will be summarized using counts and percentages. The number and percentage of patients with medical history events will be summarized. Also, the number and percentage of patients with a history of smoking (current smoker, ex-smoker, never been a smoker) will be given.

Disease related baseline characteristics will be summarized using counts and percentages as follows:

- Previous renal surgery
- On dialysis
- Kidney affected
- Index lesion an incidental or symptomatic finding
- Recurrent disease
- Total number of lesions subjected to cryoablation
- Biopsy performed on the lesion to be treated during the cryoprocedure for the study (note: if multiple lesions were treated, each lesion may not have individual biopsy results)
- At least one malignant lesion by frozen section pathology; a response of “Malignant” in the eCRF field of “What is the frozen section pathology result?” will be classed as a “Yes” for this endpoint, and responses of “Benign”, “Not otherwise specified”, or “Not Done” will be classed as a “No”.
- At least one malignant lesion by permanent section pathology; a response of “Malignant” in the eCRF field of “What is the permanent section pathology result?” will be classed as a “Yes” for this endpoint, and responses of “Benign”, “Not otherwise specified”, or “Not Done” will be classed as a “No”.

Maximum lesion size, using the greatest trans-axial diameter, will be summarized with descriptive statistics and also as categories of ≤ 4 cm and > 4 cm. The maximum lesion volume will also be summarized.

The following lab parameters will be summarized with descriptive statistics:

- eGFR
- sCR; will also be summarized separately for patients with a history of hypertension, for patients with a history of diabetes, for patients with a

history of both hypertension and diabetes; and by NS categories at baseline of low, moderate and high complexity (as defined in Section 6.3).

- Blood urea nitrogen (BUN)
- White blood cell (WBC)
- Hematocrit
- Hemoglobin
- Platelets
- Alanine aminotransferase (ALT)
- Aspartate aminotransferase (AST)
- Alkaline phosphatase (serum) (ALP)
- Alkaline phosphatase (plasma) (AKP)
- Total bilirubin (TBIL)
- International normalized ratio (INR)
- Prothrombin time (PT)
- Partial thromboplastin time (PTT)

CKD stages at baseline will be summarized with counts and percentages.

The total NS at baseline will be summarized with descriptive statistics, and also according to the categories of low, moderate and high complexity (as defined in Section 6.3). The individual R, E, N, A and L components of the NS will be summarized with counts and percentages. NS at baseline will also be summarized separately for patients with a history of hypertension, for patients with a history of diabetes, and for patients with a history of both hypertension and diabetes.

The following lesion characteristics will be summarized in a per-lesion summary (i.e., over the total number of lesions recorded in the study for descriptive statistics, and as a percentage of the total number of lesions for categorical data):

- Lesion size, by greatest trans-axial diameter, will be summarized with descriptive statistics and also as categories of ≤ 4 cm and > 4 cm
- Lesion volume will be summarized with descriptive statistics
- Duration (months) between date of baseline imaging and date of cryoprocedure will be summarized with descriptive statistics
- The type of imaging used (CT, MRI, ultrasound)
- Lesion location
- Lesion classification
- Lesion shape
- Cystic or solid lesion
- Hounsfield units, separately for each of following phases
 - Non-contrast
 - Arterial Phase
 - Venous Phase
 - Delayed Phase

- Area suspicious for lesion recurrence according to Hounsfield units (as defined in Section 6.3)
- The following biopsy related data will be summarized for all patients and separately by each site
 - Biopsy performed?
 - Duration (months) between date of biopsy sample and date of cryoprocedure will be summarized with descriptive statistics
 - Type of biopsy
 - If a core biopsy was performed, number of cores taken
 - Frozen section pathology result
 - Frozen section pathology classification
 - Permanent section pathology result
 - Permanent section pathology classification
 - Fuhrman classification grade

8.5 Prior Medications and Therapies

Frequency counts and percentages will be provided to summarize the classes of prior medications and therapies recorded on the eCRF.

8.6 Analysis of Efficacy Parameters

8.6.3 *Change in lesion size*

Change from baseline and percentage change from baseline in lesion size will be summarized with descriptive statistics for each follow-up visit. This will be done separately for greatest trans-axial diameter and for lesion volume. A per-lesion and a per-patient analysis of change in lesion size will be provided.

Waterfall plots of the percentage change in the lesion size, as measured by greatest trans-axial diameter, will be given for each follow-up visit.

8.6.4 *Post-cryoablation lesion recurrence with enhancement and lesion progression with enhancement*

The number and percentage of patients with post-cryoablation lesion recurrence with enhancement, and the number and percentage of patients with post-cryoablation lesion progression with enhancement, (as defined in Section 6.4.2) will be given for each follow-up visit. The percentage will be based on the number of patients who remain in follow-up at that visit (i.e. excluding patients who have withdrawn, died or completed after the end date of the analysis window). For example, if a patient withdrew from the study or died within the 36 month analysis visit window, the patient would be included in the 36 month visit percentage calculation, but would not be included in the percentage calculations for subsequent visits.

This analysis will also be performed for the following subgroups:

- NS complexity categories at baseline
- Procedure method
- Lesion size at baseline, by greatest trans-axial diameter, as categories of ≤ 4 cm and > 4 cm
- Comorbidities (human immunodeficiency virus [HIV]/immunocompromised; diabetes; hypertension; obesity; blood clotting disorder; abdominal surgery; cardiovascular; retroperitoneal surgery; von Hippel-Lindau; cancer, other than renal)
- Patients who did and did not receive subsequent cryoablation (note: these patients will need to be identified manually from the response to the ‘Specify type of local or systemic therapy’ field on the ‘Follow-up/Further cancer therapy’ eCRF page)
- Area suspicious for lesion recurrence (yes, no) (as defined in Section 6.4.1) at the same post-cryoablation visit
- Baseline lesion classification (i.e., exophytic, mesophytic, endophytic)

A statistical comparison between post-cryoablation lesion recurrence with enhancement (yes, no) based on the lesion status and area suspicious for lesion recurrence (yes, no) based on the Hounsfield units will be performed using Fisher’s exact test separately for each post-cryoablation visit.

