7.5. Ongoing Follow-Up Visits

It is anticipated that each subject will be seen at least once per year for a follow-up check-up.

The following follow-up data, as available, will be collected for each subject:

- Potentially related or directly related delayed cryoablation adverse events
- Lab assessments (creatinine, estimated GFR)
- Imaging results
- Biopsy/pathology results if available
- Assessment of disease progression, including retreatment
- Emergence of a new renal lesion
- Emergence of new neoplastic disease (any type)
- Emergence of metastatic disease
- Quality of Life Assessment (SF-12) at 6 and 12 months post procedure

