8.2. Missing Data

As TRACE is an observational registry of subjects and does not strictly define post-cryoablation subject follow-up, the frequency, volume and extent of data collected for each enrolled subject will vary. Missing data will not be imputed.

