4 STUDY DESIGN

4.1 General Design

This is an observational, open-label, single-arm, multi-center study of patients who have undergone renal lesion cryoablation per their physician's standard of care via a Galil Medical cryoablation system using Galil Medical needles.

Data for patients who agree to participate are collected prospectively. (i.e., registry data collection).

TRACE is anticipated to enroll approximately 250 patients at approximately 10 sites.

Patients will be enrolled from a mix of academic and community-based sites.

The schedule and number of follow-up visits for each patient will be determined by his/her physician's standard of care.

Within this context, semi-annual to annual follow-up during the five-year follow-up period is anticipated though it is recognized that follow-up schedules will vary among enrolled patients. Planned per-patient follow-up is 5 years.

The results generated by the registry database will evaluate the use, safety and effectiveness of cryotherapy for renal lesions and will assess the potential advantages and disadvantages of the procedure (e.g., disease recurrence or progression, disease-specific survival rates, overall survival rates, etc).

It will also provide information on long-term surveillance of patients undergoing renal lesion cryoablation.

In addition, this registry may be used as a continuous quality improvement tool on behalf of the treating physicians and will contribute to the development and refinement of standards of care for treatment and follow-up assessments.

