7.3 Handling of Dropouts or Missing Data

Dropout patients will not be replaced in this study. The handling of missing data will be discussed throughout Section 8, where relevant. Censoring for the efficacy endpoints is discussed in Sections 6.4.1 and throughout Section 8, where applicable.

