8.6.6.1 Time to Recurrence (TTR)

TTR will be computed as

$$\text{TTR (Months)} = (\text{Date of event/censor} - \text{Date of cryoprocedure} + 1) / 30.4375.$$

Censoring will be performed in the following order:

- 1) If a patient does not have a baseline lesion assessment, then the TTR time will be censored at the date of cryoprocedure, regardless of whether or not recurrence was observed after treatment.
- 2) If a patient has recurrence but has two or more missing lesion assessment visits (according to the 6 to 60 month analysis visits in Section 6.2.2) immediately before recurrence was observed, the TTR time will be censored at the date of the post treatment lesion assessment that occurred immediately before the first of the missed visits. For example, if a patient had a lesion assessment at Month 6, but did not have an assessment at Months 12 and 24, and then had recurrence at the Month 36 assessment, then the TTR time would be censored at the date of the Month 6 assessment.
- 3) If a patient is known not to have recurrence, the TTR time will be censored at the last date of lesion assessment date, or at the date of cryoprocedure if the patient does not have any post-treatment lesion assessments.

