8.6.9 Additional efficacy assessments

8.6.9.1 Lesion status

Lesion status (i.e., responses to the question “What is the status of the lesion?” in the follow-up lesion assessment eCRF page), will be summarized separately for each follow-up visit, as count and percentage in a per-lesion analysis. The number and percentage of lesions for each category will be given, together with a 95% CI based on Wilson (1927).

This analysis will also be performed separately

- For patients with <3 freeze cycles and <3 thaw cycles
- By procedure method (laparoscopic and percutaneous)
- By procedure method (laparoscopic and percutaneous) in patients with <3 freeze cycles and <3 thaw cycles
- By needle type (Needles with the cautery feature [IceRod CX, IceFORCE 2.1 CX, and IcePearl 2.1 CX] vs other types)

The following baseline results will be provided for lesions with a status of ‘No longer present’ at any follow-up visit:

- Number and percentage of lesions that are cystic or solid at baseline
- Baseline lesion size, by greatest trans-axial diameter, will be summarized with descriptive statistics and also as categories of ≤ 4 cm and > 4 cm
- Number and percentage in each frozen section pathology result category at baseline
- Number and percentage in each permanent section pathology result category at baseline

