8.8 Other Analyses

8.8.1 Post-treatment lesion characteristics

The analyses described in this section will be performed on the ITT and RCC populations.

The following lesion characteristics will be summarized in a per-patient summary, separately for each post treatment visit:

- Duration (months) between date of cryoprocedure and date of imaging will be summarized with descriptive statistics
- The type of imaging used (CT, MRI, ultrasound)
- Number of new lesions identified which were not present at baseline
 - Number of new lesions that are ipsilateral
 - Number of new lesions that are contralateral

The following lesion characteristics will be summarized in a per-lesion summary, separately for each post treatment visit (i.e., over the total number of lesions recorded in the study for descriptive statistics, and as a percentage of the total number of lesions for categorical data):

- Lesion in right or left kidney (right, left)
- Lesion size, by greatest trans-axial diameter, will be summarized with descriptive statistics and also as categories of ≤ 4 cm and > 4 cm
- Lesion volume will be summarized with descriptive statistics
- The type of imaging used (CT, MRI, ultrasound)
- Lesion location
- Lesion classification
- Lesion shape
- Cystic or solid lesion
- Hounsfield units, separately for each of following phases
 - Non-contrast
 - Arterial Phase
 - Venous Phase
 - Delayed Phase
- Area suspicious for lesion recurrence according to Hounsfield units (as defined in Section 6.4.1)
- Biopsy performed?
- Duration (months) between date of cryoprocedure and date of biopsy sample will be summarized with descriptive statistics
- Type of biopsy
- If a core biopsy was performed, number of cores taken
- Frozen section pathology result
- Frozen section pathology classification
- Permanent section pathology result
- Permanent section pathology classification
- Fuhrman classification grade

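### SAP 8.6.4 counts patients with no lesion assessment as event-free, so its overall visit-wise percentages are lower bounds and its subgroup percentages mix event rate with assessment rate

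*SAP*

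**What the plan says.** SAP 6.4.2 makes a lesion an event only where the follow-up lesion assessment page gives its status as recurrent (or progressing) and answers yes on contrast enhancement. For the per-patient analysis, only the lesion with the largest trans-axial diameter counts.

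SAP 8.6.4 tabulates patients with each event at each follow-up visit, overall and by seven subgroup factors. On the denominator: "The percentage will be based on the number of patients who remain in follow-up at that visit". Only withdrawal, death or completion removes a patient, and someone who leaves during a window still counts for that window. Having been assessed is not a condition.

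On missing data, Protocol 8.2 says: "Missing data will not be imputed". SAP 7.3 says: "The handling of missing data will be discussed throughout Section 8, where relevant". Section 8.6.4 then gives no rule for patients without an assessment.

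On the schedule, Protocol 7.5 says: "It is anticipated that each subject will be seen at least once per year for a follow-up check-up". SAP 4.1 expects semi-annual to annual follow-up and adds that "it is recognized that follow-up schedules will vary among enrolled patients".

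Three other planned tables bear on this:
- SAP 8.1 counts patients with a lesion assessment in each window, over the same in-follow-up denominator.
- SAP 8.6.9.1 reports lesion status, which "will be summarized separately for each follow-up visit, as count and percentage in a per-lesion analysis".
- SAP 8.8.1 introduces a list that includes imaging type: "The following lesion characteristics will be summarized in a per-patient summary, separately for each post treatment visit".

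**The concern.** Being in follow-up and having been assessed are different states, and SAP 8.1 treats them so: it reports the second as a percentage of the first. Section 8.6.4 takes its numerator from the second group and its denominator from the first. An unassessed patient therefore has the same numerical effect as a patient scanned and found clear.

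The SAP handles the same gap differently elsewhere. In the time-to-recurrence example (8.6.6.1), a patient has a Month 6 assessment, "but did not have an assessment at Months 12 and 24, and then had recurrence at the Month 36 assessment"; that patient is censored at Month 6. In 8.6.4 the same patient is event-free at Months 12 and 24. Technical success (6.5.1) uses the same status and enhancement fields and is set to missing if any of its fields is missing.

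Post-cryoablation lesion enhancement is a listed efficacy endpoint (6.4). Progression is no longer an event in time to recurrence (5.2), so 8.6.4 is the only planned by-visit, per-patient summary of progression with enhancement. Subgroups that are scanned at different frequencies could appear to differ in recurrence when they do not.

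**Working it through.** The plan states no event rate or assessment rate, so there is no figure to reproduce. All rates and counts in steps 2, 4 and 5 are assumptions.

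**1. The bound.** At a visit let N = patients in follow-up, n = those assessed in the window, x = recorded events, and u = events among the N − n unassessed.
- SAP percentage: x/N
- Percentage among assessed: x/n, so x/N = (x/n) × (n/N)
- Proportion among patients in follow-up: (x + u)/N

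Since u ≥ 0, x/N ≤ (x + u)/N, with equality only if u = 0.

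**2. Size under assumed values.** With 5% among assessed, the table shows:

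| Share assessed | Shown |
|---|---|
| 90% | 5% × 0.9 = 4.5% |
| 80% | 5% × 0.8 = 4.0% |
| 60% | 5% × 0.6 = 3.0% |
| 50% | 5% × 0.5 = 2.5% |

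With N = 200, n = 120, x = 6: 6/200 = 3.0% shown, against 6/120 = 5.0% among assessed. If the 80 unassessed have the event at 0%, 2.5%, 5% or 10%, then (6 + 80 × rate)/200 = 3.0%, 4.0%, 5.0% or 7.0%.

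**3. Which windows the schedule leaves empty (SAP 6.2.2, procedure = day 1).**
- Annual scans fall near days 366, 731, 1097, 1462 and 1827, one in each of Months 12 to 60. None falls in Month 6 (days 93–275).
- Semi-annual scans (184, 366, …) reach Month 6 and every window to Month 60.
- Neither schedule reaches Pre 6 Month (days 1–92), which stays empty unless an early scan is done.
- An annual scan leaves Month 12 (276–549) only if at least 366 − 275 = 91 days early or 550 − 366 = 184 days late. It leaves Months 24 to 60 only if at least 180–182 days early or 185–187 days late.

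Months 12 to 60 are therefore affected only by missed or badly displaced scans.

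**4. Month 6 from the schedule alone.** If 25%, 50% or 75% of patients are imaged strictly annually and all others are scanned in the window, 5% among assessed is shown as 5% × 0.75 = 3.75%, 5% × 0.50 = 2.5% or 5% × 0.25 = 1.25%.

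**5. Subgroups.** Two groups with the same 5% among assessed, one 90% and the other 60% assessed, show 4.5% and 3.0%. Of the seven factors:
- The Hounsfield factor is defined at the same visit, so unimaged patients cannot be classified; the effect there is small or absent.
- Procedure method is partly covered by 8.6.9.1, per lesion and without the enhancement condition.
- For the other five (nephrometry complexity, lesion size, comorbidities, subsequent cryoablation, lesion classification) no number assessed is planned.

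**6. The bracket in 8.6.4 and 8.1.** Take a withdrawal on day 1100. Read literally, the bracket excludes patients who left after the window's end. That drops Pre 6 Month and Months 6, 12 and 24 (ends 92, 275, 549, 915) and keeps Months 36, 48 and 60. The worked example beside it requires the reverse: keep all windows through Month 36, drop Months 48 and 60 (starts 1282, 1648).

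**The case against.** The strongest reply is that 8.6.4 is descriptive: it reports recorded events over an openly stated denominator, plans no confidence interval for these percentages, and sits in a registry that SAP 4.4 says is not powered for formal analysis. The overall assessed-only figure is largely recoverable, because 8.6.4 gives the count and 8.1 gives the number assessed per window. That stands, and it confines the unresolved loss mainly to the subgroup tables. The shells are a separate document (SAP Section 12) and may already show the number assessed.

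A reader might infer a breach of the protocol's no-imputation rule, or a contradiction with time to recurrence. The documents do not support either. No value is assigned to anyone, and time to recurrence censors because the event time is uncertain. In the example, 8.6.4 even keeps the Month 36 recurrence that time to recurrence sets aside. The comparison shows inconsistent handling of the same gap, no more.

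A reader might also say that progression with enhancement appears nowhere else. Technical success (6.5.1, 8.7.1) uses it too, but pools it with recurrence and covers only the first imaging.

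Nor is the largest-lesion rule in 6.4.2 simply an error because 6.4.4 counts any lesion: it is the per-patient rule throughout 6.4.1 to 6.4.3. On the bracket, the worked example settles the intent, so that change is a clarification.

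**Conclusion.** The point holds as a reporting defect worth correcting. Reading the count as events recorded in that window, each overall 8.6.4 percentage is a lower bound on the proportion with the event among patients in follow-up, with respect to missing assessments only. It is not a bound against sampling error, misread scans or events in patients who have left follow-up. If everyone is assessed, it is exact.

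The size cannot be stated, because the documents give no assessment rate; 3.0% against 5.0% is an illustration. It would be tempting to conclude that the registry's recurrence results as a whole are understated. That does not follow: Kaplan-Meier time to recurrence and its Cox models do not use this denominator, and Months 12 to 60 lose nothing if scans keep to the anticipated schedule. Nor is the assessed-only percentage the true one, since it can overstate if scans are prompted by suspicion.

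What remains is that, for five subgroup factors, a difference in percentage cannot be told apart from a difference in assessment.

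**What to change.** For each visit and each subgroup in 8.6.4:
- show the number in follow-up, the number with a non-missing lesion status and the number not assessed;
- give the percentage among assessed beside the in-follow-up percentage;
- footnote that the in-follow-up figure treats unassessed patients as event-free, and that the assessed-only figure may overstate if suspicion prompts scanning.

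In 8.6.4 and 8.1, reword the bracket so that it removes patients who withdrew, died or completed before the window starts, in line with the worked example.

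As a separate minor point, reconcile the largest-lesion rule in 6.4.2 with the any-lesion rule in 6.4.4, for example by also showing the any-lesion count.

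The cost is SAP wording and a table re-run on data already collected. The downsides are a larger table, a smaller denominator for the assessed-only figure, and possible overstatement in it. If the shells already show the number assessed, only the second percentage, the footnote and the wording changes remain.

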8 STATISTICAL ANALYSIS

8.1 Disposition of Patients

The number of patients enrolled will be summarized by analysis population (see Section 8.3) and by site. The number of patients who completed the study, the number of patients ongoing in the study (for interim analyses), and the number of patients who discontinued from the study and the reasons for discontinuing (e.g., withdrew consent, lost to follow-up, death, other) will also be summarized.

Duration of follow-up is defined as the time from cryoprocedure until date of death due to any cause or date when patient was known to be alive.

Duration of follow-up (months) =

$$(\text{Date of death/last known alive} - \text{Date of cryoprocedure} + 1) / 30.4375$$

Duration of follow-up will be summarized using descriptive statistics. The number and percentage of patients with follow-up up to the following timepoints will also be provided:

- 1 month
- 3 months
- 6 months
- 12 months
- 24 months
- 36 months
- 48 months
- 60 months.

The number of patients who have completed each follow-up visit will be provided based on the analysis windows derived from the lesion assessment follow-up dates. The corresponding percentage of patients will be based on the number of patients who remain in follow-up at that visit (i.e. excluding patients who have withdrawn, died or completed after the end date of the analysis window). For example, if a patient withdrew from the study or died within the 36 month analysis visit window, the patient would be included in

the 36 month visit percentage calculation, but would not be included in the percentage calculations for subsequent visits.

The number of patients censored for the time-to-event endpoints, together with a breakdown of the reasons for censoring, will also be summarized.

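### SAP 8.1 and 8.6.4: on its natural reading, the parenthesis defining who is still in follow-up at a visit excludes the wrong patients in every window except the one in which a patient leaves

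*SAP*

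**What the plan says.** SAP 8.6.4 sets the denominator for recurrence with enhancement and for progression with enhancement at each follow-up visit: "The percentage will be based on the number of patients who remain in follow-up at that visit". A parenthesis then spells out what that means: "excluding patients who have withdrawn, died or completed after the end date of the analysis window". A worked example follows. It supposes that "if a patient withdrew from the study or died within the 36 month analysis visit window", and concludes that "the patient would be included in the 36 month visit percentage calculation, but would not be included in the percentage calculations for subsequent visits". The same analysis is repeated for seven sets of subgroups.

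SAP 8.1 uses the same parenthesis and the same example for the percentage of patients completing each follow-up visit.

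The windows are in SAP 6.2.2, counted from the cryoprocedure as day 1. SAP 4.1 states: "Planned per-patient follow-up is 5 years".

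**The concern.** A patient who withdraws, dies or completes after a window has closed was in follow-up for the whole of that window. That patient belongs in the denominator, yet the parenthesis takes the patient out. A patient who left before the window opened could not have been assessed in it, yet nothing in the parenthesis removes that patient.

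If a programmer codes the parenthesis as written, two families of tables change: visit completion, and recurrence and progression by visit, overall and by subgroup. Patients counted in the numerator need not be in the denominator, so a percentage can even exceed 100%. Completers are the least protected group, because the example deals only with withdrawal and death.

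**Working it through.** The documents give no figure to reproduce here, so the check has two parts: the logic for single patients, then the size under stated assumptions.

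**Step 1. Two rules, three patients.** For a window running from day *s* to day *e*:

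- Parenthesis, natural reading: count the patient if exit day ≤ *e*.
- Lead phrase and example: count the patient if exit day ≥ *s*.

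Windows (SAP 6.2.2): Pre 6 Month 1–92; 6 Month 93–275; 12 Month 276–549; 24 Month 550–915; 36 Month 916–1281; 48 Month 1282–1647; 60 Month 1648–2013. Five years is 5 × 365.25 ≈ day 1826, inside the 60 Month window.

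| Exit | Counted under the parenthesis | Counted under lead phrase and example | Agree in |
|---|---|---|---|
| Day 200, drop-out | 6 to 60 Month | Pre 6 and 6 Month | 6 Month only |
| Day 1100, drop-out | 36, 48, 60 Month | Pre 6 to 36 Month | 36 Month only |
| Day 1826, completer | 60 Month only | Pre 6 to 60 Month | 60 Month only |

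The day-1100 patient is the SAP's own example. The two rules agree at 36 months and give opposite answers in every other window. For the completer, day 1826 is later than day 1647, so the parenthesis removes the patient from all windows through 48 months.

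**Step 2. Size.** N = 250 is the approximate planned enrolment (SAP 4.1). Attrition is an assumption: a constant rate *a* of 5%, 10% or 15% per year, with everyone remaining completing on day 1826.

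- Intended denominator: N × (1 − *a*)^((*s* − 1)/365.25).
- Literal denominator: N × [1 − (1 − *a*)^(*e*/365.25)] for *e* < 1826, and N once *e* ≥ 1826.

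At 36 months with *a* = 5%: intended 250 × 0.95^(915/365.25) = 219.9; literal 250 × [1 − 0.95^(1281/365.25)] = 41.2.

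Expected denominators, intended / literal:

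| Window | 5% per year | 10% per year | 15% per year |
|---|---|---|---|
| 6 Month | 246.8 / 9.5 | 243.5 / 19.1 | 240.0 / 28.8 |
| 12 Month | 240.5 / 18.6 | 230.9 / 36.6 | 221.2 / 54.2 |
| 24 Month | 231.4 / 30.1 | 213.4 / 58.0 | 195.8 / 83.6 |
| 36 Month | 219.9 / 41.2 | 192.0 / 77.2 | 166.4 / 108.6 |
| 48 Month | 208.8 / 51.6 | 172.8 / 94.5 | 141.4 / 129.9 |
| 60 Month | 198.4 / 250.0 | 155.5 / 250.0 | 120.1 / 250.0 |

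The error changes direction. The literal denominator is too small through 48 months and too large at 60 months. At 36 months, only about 11, 19 or 25 of the patients in the literal denominator left inside the window; the rest had gone before it opened.

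**Step 3. Effect on a percentage.** Assume ten recurrences recorded at 36 months. The intended rule gives 4.5%, 5.2% or 6.0% at 5%, 10% or 15% attrition. The literal rule gives 24.3%, 12.9% or 9.2% (unrounded denominators). At 6 months with 5% attrition, ten events over 9.5 patients is 105.6%. These percentages keep all ten events in the numerator whatever the denominator; a programmer who also restricted the numerator would get different values.

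**Step 4. Does another parse rescue the text?** Suppose the date condition attaches only to completion. Then anyone who ever withdrew or died is excluded everywhere, including at 36 months in the example, and completers still vanish from the earlier windows. That reading fails too.

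**The case against.** The strongest reply is that the intent is stated on both sides of the parenthesis, by the lead phrase before it and the example after it, so a careful programmer would code it correctly. This largely stands for withdrawals and deaths. For completers, only the lead phrase points the right way.

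A reader might infer that rule and example are irreconcilable. The documents do not support that. They agree for the window in which a patient leaves. A strained parse, in which leavers are excluded once the window in which they left has ended, also fits the example throughout. The words do not naturally say this, because the window mentioned is most easily taken as the one being summarised.

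A reader might also infer that the literal denominators contain only people who have left. That is too strong: patients with no recorded exit, such as those ongoing at an interim analysis (SAP 8.1), stay in. The illustration gives everyone an exit date, which widens the contrast.

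Nor do the documents show that any table is wrong. SAP 5.2 records Steering Committee review of draft outputs dated 08 May 2018, including changes to the enhancement tables. A 6-month denominator of 10 to 29 out of 250 would probably have been noticed. That makes literal coding less likely, but neither the program nor the table shells are available to settle it.

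**Conclusion.** The parenthesis is wrong as written in both sections. On its natural reading it contradicts the lead phrase in every window but the exit window, and contradicts the example at the later visits that the example addresses. This follows from the text and the SAP 6.2.2 windows and needs no assumption about attrition.

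The size is conditional on literal coding and on attrition. For 250 patients and assumed attrition of 5% to 15% per year, the 36-month denominator would be about 41 to 109 instead of about 220 to 166.

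The reach is limited to descriptive visit percentages: visit completion, and recurrence and progression with enhancement, overall and by subgroup. A reader might extend the point to the long-term recurrence and survival estimates. That does not follow: Kaplan-Meier time to recurrence, disease-specific survival and overall survival have their own event and censoring rules in SAP 8.6.6 and do not use this denominator.

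**What to change.** In SAP 8.1 and SAP 8.6.4, replace the parenthesis with: *excluding patients who withdrew, died or completed before the start date of the analysis window*. Keep the example, which then agrees with the rule. The new wording also settles completers: someone finishing on day 1826 counts in every window through 60 Month and drops out only of Post 60 Month.

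Then check that the programmed condition compares the exit date with the window's start date. The cost is one phrase in two sections and one programming check; no data collection or other analysis changes.
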